10. STUDY CONDUCT CONSIDERATIONS

10.1. Regulatory and Ethical Considerations, Including the Informed Consent Process

10.1.1. Ethics Committee opinion

It is the responsibility of the Sponsor to seek and obtain the favorable opinion of the CPP (Independent Ethics Committee).

The present trial will not be initiated until this favorable opinion is obtained.

10.1.2. ANSM authorisation

It is the responsibility of the Sponsor to seek and obtain the authorization from ANSM (Agence Nationale de Sécurité du Médicament) for conducting the trial.

The present trial will not be initiated until the ANSM authorization is received.

10.1.3. Protocol Amendments

Any significant change (substantial modification) in the study requires a protocol amendment sent to ANSM and/or CPP. The investigator must not make any changes to the study without regulatory authorities and sponsor approval except when necessary to eliminate apparent immediate hazards to the subjects.

10.1.4. Regulatory requirements and ethical considerations

In compliance with French law, according the articles R1121-10 to R1121-15 of the Public Health Code (Code de Santé Publique), an approval as a site for Phase 1 biomedical research was granted to the clinical unit by the regional Agency of Health (ARS) (Renewal numbers N° 2017-02 for CIC-CPCET, N°2017-8358 for Eurofins|Optimed)

The study will be conducted in accordance with all applicable regulatory requirements and in accordance with ICH Good Clinical Practice (GCP E6 R2), all applicable subject privacy requirements, and the guiding principles of the Declaration of Helsinki (last amendment 2013).

Written informed consent must be obtained from each subject prior to participation in the study. Two Informed Consent forms will be prepared, one for the SAD part and one for the MAD part. The form for the MAD, updated before implementation of this part, with the safety and PK results collected during the SAD part and with the MAD planned dose levels, will be submitted to the CPP.

Subjects will be informed by an investigator of all pertinent aspects of the trial: the purpose of the study, the study drug, the trial procedures to be followed, including all invasive procedures, its possible risks and restrictions, the duration of subject's participation, and the fee that they will receive. Each subject must be informed that participation in the study is voluntary and that he may withdraw from the study at any time, that records identifying the subjects will be kept in confidential manner, except for the trial monitor and the regulatory authorities which will be granted direct access to medical records for verification of data and study procedures, and that data collected on CRFs during the study will be documented in an pseudonymous fashion. An information sheet will be given to each subject. The language used in the oral and written information about the trial and written informed consent form, should be easily understandable to the subject.

Before informed consent may be obtained, the investigator should provide the subject ample time and opportunity to inquire about details of the trial and to decide whether or not to participate in the trial. The subject should carefully read before signing and dating the informed consent form. The informed consent form must be signed and personally dated by both the subject and the investigator. A copy of the signed document should be given to the subject. A copy will be kept for 15 years by the investigator (the second copy given to the subject).

Whenever important new information becomes available that may be relevant to the subject's consent, the written subject information sheet and any other written information provided to subjects will be revised by the sponsor and be submitted again to the Ethics committee for review and approval. The approved, revised information will be provided to each subject in the trial for signing and dating. The Investigator will explain the changes to the previous version.

10.1.5. *Subject confidentiality*

All personal data collected and processed for the purposes of this study should be managed by the Investigator and his/her staff with adequate precautions to ensure confidentiality of those data, and in accordance with the Health Insurance Portability and Accountability Act applicable to French national laws and regulations on personal data protection and the General Data Protection Regulation n° 2016/679.

Monitors, auditors, and other authorized agents of the sponsor and/or its designee, the ethics committee approving this research, and ANSM, as well as those of any other applicable agency, will be granted direct access to the study subjects' original medical records for verification of clinical study procedures and/or data, without violating the

confidentiality of the subjects to the extent permitted by the law and regulations. In any presentations of the results of this study or in publications, the subjects' identity will remain confidential.

10.1.6. *Urgent Safety Measures*

If an event occurs that is related to the conduct of the study or the development of the study treatment, and this new event is likely to affect the safety of subjects, the sponsor and the investigator will take appropriate urgent safety measures to protect subjects against any immediate hazard. See paragraph 8.3.

10.2. **Quality Assurance and Quality Control**

10.2.1. *Monitoring*

The study will be monitored by the CRO Qualissima.

In accordance with GCP, the monitor, representative of the sponsor will monitor the study and site activities to verify that the:

- Data are authentic, accurate, and complete.
- Safety and rights of subjects are being protected.
- Study is conducted in accordance with the currently approved protocol and any other study agreements, GCP, and all applicable regulatory requirements.

The monitor will check that the CRFs have been correctly completed, with comparison of source documents and check that AEs have been documented.

Source data must be available at the study site to document the existence of the research subjects and to substantiate the integrity of study data collected. Source data must include the original documents relating to the study, as well as the medical treatment and medical history of the subject.

The investigator agrees to allow the monitor direct access to all relevant documents.

This study will be monitored at regular intervals, by mutual agreement of the investigator and the monitor.

10.2.2. *Audit/Inspection*

The Sponsor or its representative may conduct audits at the investigative site, before, during or after the study. The Regulatory Authorities may also carry out an inspection at any time. In this case, the Investigator must inform the Sponsor as soon as he receives the notification of inspection.

The investigator must allow the auditor(s) and inspector(s) to:

- Inspect the site, facilities and material used for the study,
- Meet the members of the team involved in the study,

- Have direct access to study data and source documents,
- Consult all relevant documents

10.2.3. *Study and Site Closure*

Upon completion or premature discontinuation of the study, the monitor will conduct site closure activities with the investigator or site staff, as appropriate, in accordance with applicable regulations and GCP.

In addition, the sponsor reserves the right to temporarily suspend or prematurely discontinue this study at any time for reasons including, but not limited to, safety or ethical issues or severe non-compliance.

10.2.4. *Records Retention*

Following closure of the study, the investigator must maintain all site study records and investigator file, in a safe and secure location. The records must be maintained to allow easy and timely retrieval, when needed (e.g., audit or inspection), and, whenever feasible, to allow any subsequent review of data in conjunction with assessment of the facility, supporting systems, and staff.

To comply with all applicable regulatory requirements, the minimum retention time will be not less than 15 years.

10.3. **Report and Publication**

10.3.1. *Report*

The results of the study will be reported in a Clinical Study Report. This report will be prepared by the investigational site according to the guidance ICH E3 “Structure and Content of Clinical Study Report”.

10.3.2. *Publications*

[figure not shown]
The sponsor must review and approve any results of the study or abstracts for professional meetings prepared by the Investigator(s). Published data must not compromise the objectives of the study.

12. APPENDICES

12.1. Appendix 1: Liver Safety Algorithms

12.2. Appendix 2: Stopping rules

Stopping rules	Individual subject	Within a cohort/dose escalation
ALT or AST $\geq 3 \times$ ULN	1 subject	
ALT or AST $> 5 \times$ ULN		2 subjects
Triglycerides ≥ 5.6 mmol/L	1 subject	2 subjects
Creat $> 1,2 \times$ ULN or Increase in serum creat by $\geq 30 \mu\text{mol/L}$ within 24h or Increase in serum creat to $\geq 1,5 \times$ baseline within 7 days	1 subject	2 subjects
$\beta 2$ microglobuline $\geq 2 \times$ ULN	1 subject	2 subjects
Hematuria $> 2+$ on dipstick verified by cytologic exam, on 2 samples and considered at least possibly related to the IMP	1 subject	2 subjects
QTcB and QTcF > 500 msec or Change from baseline: QTc > 60 msec	1 subject	2 subjects
HR < 45 or HR > 130 bpm*	1 subject	2 subjects
SBP < 80 or SBP > 155 mmHg	1 subject	2 subjects
DBP > 100 mmHg	1 subject	2 subjects
Occurrence of a Serious Adverse Event considered at least possibly related to the IMP administration	1 subject	1 subject
Possibly drug related severe AEs in the same cohort, independent of within or not within the same system-organ		2 subjects
Clinically significant drug-related laboratory abnormalities of the same character		2 subjects
AUC _(0-inf) > 111.14 ng/ml.h ⁻¹ or Cmax > 23.77 ng/ml		1 subject (only for dose escalation)

* When resting heart rate is between 60-100 beats per minutes. Use clinical judgment when characterizing bradycardia among some healthy subject populations, for example, conditioned athletes.

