	
• Tympanic body temperature: on D-1; D1 pre-dose, 1.5 and 12h post first dose; on D2, D4, D6, D8, D10 and D12 every morning before dosing; on D14 at pre dose, and 1.5, 12h post dose; on D17 before discharge; FU• ECG on D-1; D1 at pre-dose (in triplicate) and 1, 2, 4, 8, 12h post first dose; D3, D6, D10 and D13 in the morning before dosing and D17 at discharge; FU• Laboratory evaluation: haematology, coagulation and biochemistry on D-1, D3, D6, D10 and D13 in the morning before dosing and D17 at discharge; FU; urinalysis on D-1; D1 at pre-dose, D3, D6, D10 and D13 in the morning before dosing and D17 at discharge; FU• Vigilance (Bond and Lader VAS) on D1 pre-dose and 1.5, 12h post dose; on D14 pre dose and 1.5, 12h post dose 
Pharmacokinetic Assessments in blood
 
◆ SAD
 
First cohort (dosing in the morning): blood sampling for PK of IFB-088 and its metabolite at pre-dose and 0.16, 0.33, 0.5, 0.75, 1, 1.5, 2, 2.5, 3, 4, 5, 8, 12, 24 and 32h post dose
 
From Cohort 2 (daily dose separated in 2 administrations with a 12-hour interval): blood sampling for PK of IFB-088 and its metabolite at pre-dose and 0.33, 0.66, 1, 2, 3, 4, 5, 12, 12.25, 12.5, 13, 14, 16, 18, 24 and 32h post morning dose
 
◆ MAD
 
Blood sampling for PK of IFB-088 and its metabolite at D1 and D14 pre-dose and 0.5, 1, 2, 3, 4, 6, 8, 10, 12, 13, 14, 17, 19 and 21h post morning dose; D2 24h post first dose just before the morning administration; D7 pre dose, 1h and 2 h post dose, D15 at 24, 30, 36 and 42h post D14 morning dose; D16 at 48h and 60h post D14 morning dose
 
Pharmacokinetic Assessments in urine
 
◆ SAD
 
Urine sampling for PK of IFB-088 and its metabolite IFB-139: Cohort 1: pre-dose and 0-4, 4-8, 8-16, 16-32 h post-dose intervals. From Cohort 2: pre-dose and 0-4, 4-8, 8-12, 12-24, 24-32h post-dose intervals
 
◆ MAD
 
Urine sampling for PK of IFB-088 and its metabolite: on D1 and D14: at pre-dose and 0-4, 4-12, 12-24 h post first dose; D6 at pre-dose, 0-4 and 4-12h; D15 at 24-36 and D16 at 36-48h post D14 morning dose
 
Biomarker assessments (exploratory)
 
There is currently no validated specific biomarker. So subjects will be asked to donate blood samples that could be used as healthy controls for research purposes in patients. A specific part in the informed consent will be signed. This assessment will be performed only for SAD part.
 
◆ SAD
 
Samples will be drawn at specific time points: Pre-dose, 1.5h and 24h post dose
 
• One sample (3 ml) on heparin lithium tube for PBMC extraction• One sample (2.5ml) on PAXgene tube for RNA extraction 
Samples will be stored in the CRB (Centre de Ressources Biologiques) at -150°C for 5 years after final database freeze and then destroyed.

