- The C_{max} reaches 23.77 ng/ml.h (half of the C_{max} in dogs at the NOAEL).

The maximum recommended starting dose (MRSD) for IFB-088 in adult healthy volunteers was evaluated at 2.90 mg/day in Humans.

The maximal daily dose to be administered in Humans to cover the different envisioned therapeutic indications was evaluated at 80 mg/day. Therefore, in order ensure optimal safety, **the dose ranges selected are:**

- **2.5 mg/day for the first therapeutic dose;**
- **60 mg/day given as 2 administrations of 30 mg for the highest therapeutic dose.**

1.2.3. *Dose Rationale for the MAD part*

1.2.3.1. *Update on Safety coverage*

Additional toxicology studies have been conducted in rodent (rat) and non-rodent (dog) animal species to further assess IFB-088 safety (see sections 4.3.1 & 4.3.4 of Investigator's Brochure):

- GLP repeated dose toxicity studies in Sprague Dawley rats and Beagle dogs at doses up to 12 mg/kg/day for 13 weeks. Observations and pharmacokinetic parameters of IFB-088 and its major metabolite (IFB-139) are summarized in Table 6.

Table 6: Summary of results from the GLP 13-week toxicology studies in rats and dogs

Study	Regimen	Main findings	analyte	Day of admin.	sexe	Plasma Tmax	Cmax (ng/ml)	AUCt (ng/ml*h)
46232 TSR 13-week toxicology GLP study in Sprague Dawley Rats	Repeated administration 13 weeks P.O.: 1.5 mg/kg BID (6h between the 2 treatments) 3 mg/kg/day	NOAEL	IFB-088	1	Female	T1: 30min	1.69	8.07
					Male	T1: 30min	0.79	5.86
			IFB-088	90	Female	T1: 30min	1.63	8.86
					Male	T1: 10min	0.50	3.79
			Major metabolite IFB-139	1	Female	T1: 3h	1.20	7.85
					Male	T1: 7h	0.98	7.04
	Major metabolite IFB-139	90	Female	T1: 9h	0.93	9.43		
			Male	T1: 7h	1.56	8.98		
	Repeated administration 13 week P.O.: 3 mg/kg BID (6h between the 2 treatments) 6 mg/kg/day	At 6 mg/kg/day administered as 3 mg/kg BID for 13 weeks was considered as adverse due to: - 2 out of 10 males presented enlarged kidneys, with irregular colour and/or surface; these changes correlated with the presence of crystal nephropathy at microscopic examination. - One female presented non-adverse, reversible, minimal bile duct hyperplasia. There were no other remarkable, test item-related signs at 6 mg/kg/day	IFB-088	1	Female	T1: 30min	2.95	26.4
					Male	T1: 30min	2.01	13.4
			IFB-088	90	Female	T1: 30min	2.73	29.9
					Male	T1: 10min	2.94	23.6
			Major metabolite IFB-139	1	Female	T1: 7h	1.20	15.1
					Male	T1: 3h	4.67	36.6
	Major metabolite IFB-139	90	Female	T1: 9h	2.96	36.6		

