- **50 mg/day given as 2 administrations of 25 mg in the third cohort.**

1.2.4. *Rationale for Study population*

As is usual in first-in-man studies, the population to be included is healthy young males between 18 and 40 years old (inclusive) at screening. The selection of healthy subjects is justified on the basis that PK, safety, and tolerability, can be investigated accurately in this population.

In this population, the study can be performed under standardized conditions, reducing the influence of confounding factors.

No medical benefit for the subjects can be expected beyond the thorough medical check-up that each subject will receive prior to treatment and at the end of the study. The potential risks associated with IFB-088 are not known, as this product has not yet been tested in humans.

The study protocol is designed to ensure a careful observation and medical management in order to minimize any associated risk in this study.

The participation of healthy subjects in this study is justified with regard to the expected benefit for the target population that will receive this therapy after registration of the compound.

1.3. **Summary of Risk Management**

1.3.1. *Cardiovascular Monitoring*

Since IFB-088 is devoid of alpha-2 adrenergic activity, a potent reduction in blood pressure is not expected with IFB-088. In addition, even if in vitro, in a HERK study IFB-088 was classified as a potential moderate HERK channel inhibitor, IFB-088 at 1, 3 or 9 mg/kg/day (0.5, 1.5, 4.5mg/kg/administration) had no effect on heart rate, systolic, diastolic and mean arterial blood pressure, ECG parameters or body temperature in conscious male beagle dogs and no treatment-related arrhythmias were observed at any of the dose-levels administered in dog (see Investigator Brochure [section 4.1.3.2](#) and [section 4.1.3.5](#)). Nevertheless, as usual in a first in man study a particular attention will be focused on cardiovascular monitoring. Vital signs (systolic and diastolic blood pressure, heart rate) will be closely monitored at regular intervals post dosing, both in supine and standing position and ECG parameters will be controlled at regular intervals post-dosing.

1.3.2. *Drug-induced renal crystals*

Preliminary toxicity studies pointed out renal findings after 10 or 14 days once a day administration from 10 mg/kg in dogs and rats. In particular, intratubular crystals were observed

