Moreover, the occurrence of moderate adverse reactions within the same system-organ-class in more than one subject, and/or clinically significant changes from baseline measurements will be considered as a safety signal and will have to lead to increase caution and a closer assessment of safety parameters in the other subjects. In such a case, data from all subjects would be to be reviewed.

3.4.3.1. *Liver Chemistry Stopping Criteria*

Liver chemistry threshold stopping criteria have been designed to ensure subject safety and to evaluate liver event etiology (in alignment with the FDA premarketing clinical liver safety guidance).

Study treatment will be stopped **for a subject** if the following liver chemistry stopping criteria is met:

- ALT or AST $\geq 3\text{xULN}$

Refer to Section 8.10, Liver Chemistry Follow-up Procedures, for details of the required assessments if a subject meets the above criteria.

3.4.3.2. *Triglycerides Stopping Criteria*

Several subjects experienced hypertriglyceridemia during the SAD part of the study. All cases were below the threshold of 5.6 mmol/L (i.e. 5 g/L), above which hypertriglyceridemia is considered clinically significant (European Atherosclerosis Society, European Society of Cardiology, French Society of Endocrinology) and no correlation or possible dose relationship was established. Moreover, some subjects with hypertriglyceridemia were in the placebo groups.

Nevertheless, a stopping criterion for triglycerides has been added in the MAD part of the study:

Study treatment will be stopped for a subject if the following criterion is met:

- Serum triglycerides ≥ 5.6 mmol/L and the subject is receiving IFB-088

Study treatment will be stopped for the whole cohort and the dose will not be escalated, if the following criterion is met:

- Serum triglycerides ≥ 5.6 mmol/L in 2 subjects receiving IFB-088.

Next cohort could be administered a lower dose intermediate between the previous cohort and the present cohort.

3.4.3.3. *Renal disorders*

The dose should not be escalated further if one of the circumstances listed below occurs **in 2 or more subjects** within the same cohort:

- Creatinine > 120 $\mu\text{mol/L}$ (1.2 ULN) (Grade 1)
- Or a change from baseline ≥ 30 $\mu\text{mol/L}$ within 24 h
- Or a change from baseline $\geq 50\%$ within one week

(KDIGO definition Ostermann and Joannidis, 2016)

- Hematuria $> 2+$, verified by cytologic exam, on 2 samples and considered at least possibly related to the IMP

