6. STUDY ASSESSMENTS AND PROCEDURES

This section lists the parameters of each planned study assessment. The exact timing of each assessment is listed in the Time and Events Tables ([Section 3.5](#)). Detailed procedures for obtaining each assessment are provided below.

Whenever vital signs, 12-lead ECGs and blood draws are scheduled for the same nominal time, the assessments should occur in the following order: 12-lead ECG, vital signs, blood draws. The timing of the assessments should allow the blood draw to occur at the exact nominal time.

The timing and number of planned study assessments and procedures may be altered during the course of the study based on newly available data (e.g. to obtain data closer to the time of peak plasma concentrations) to ensure appropriate monitoring. Additional safety tests (such as vital signs, physical exams, and clinical laboratory tests (up to a maximum of approximately 500 mL of blood from the subject within a 30-day period)) may also be obtained during the course of the study based on newly available data, to ensure appropriate safety monitoring.

The Ethics Committee will be informed of any safety issues that require alteration of the safety monitoring scheme.

The actual date and time should be recorded for all procedures and the Investigator should make every effort to perform procedures at the scheduled nominal dates and times.

6.1. **Demographic/Medical History Assessments**

Demographic data will include date of birth, height in centimeters, and body weight in kilograms.

Medical/medication/alcohol and drug abuse histories will be assessed as related to the eligibility criteria listed in Section 4.2 as well as life habits (tobacco, tea, coffee, chocolate and/or beverage containing caffeine).

6.2. **Safety**

Planned timepoints for all safety assessments are listed in the Time and Events Table ([Section 3.5](#)). Additional time points for safety tests (such as vital signs, physical exams and laboratory safety tests) may be added during the course of the study based on newly available data to ensure appropriate safety monitoring.

Physical Exam

- A complete physical examination will include assessments of the head, eyes, ears, nose, throat, skin, thyroid, neurological, lungs, cardiovascular, abdomen (liver and spleen), lymph nodes and extremities. Height and weight will also be measured and recorded.

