The analysis sets will be validated during the final data review meeting.

A summary of protocol deviations by treatment group and the corresponding listing by subject will be generated.

9.3.2. *Hypothesis and statistics*

No formal statistical hypothesis will be tested. Safety data including but not limited to AEs, vital signs, ECGs, and laboratory safety tests will be descriptively summarized by doses.

Estimation approach will be adopted to estimate both the between- and within-subject PK variability and to assess the dose proportionality following single dosing of IFB-088.

Descriptive statistics will be supplied according to the nature of the criteria:

- Quantitative variables: sample size, arithmetic mean, standard deviation (SD), median, minimum and maximum (with geometric mean and coefficient of variation (CV) for PK);
- Qualitative variables: sample size, absolute and relative frequencies per class.

9.3.3. *Interim Analysis and/or schedule of analyses*

No formal interim analysis is planned. During dose escalation phases, PK and safety data will be reviewed on an in-stream basis to inform the dose escalation decision.

Statistical analyses will be performed after achievement of each cohort in order to provide ongoing safety, PK data so that the DEC can have access to all information they need to decide the dose escalation. A statistical report will be generated for each DEC meeting, the content will be detailed in the DEC charter.

A final analysis will be done after SAD part and after MAD part, statistical results will be presented in the clinical study report.

9.3.4. *Handling of dropouts and missing data*

Dropout subjects will not be analyzed for pharmacokinetics.

No repositioning of visits will be done.

If not otherwise stated:

- Missing data other than baseline values will not be replaced.
- Baseline for safety parameters will be defined as the last available parameter value before and closest to the first dosing.

9.3.5. *Demographic and baseline characteristics*

The following analysis will be performed on the Randomized set.

The subjects' demographic and baseline characteristics will be summarized by treatment group and listed by subject.

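### MAD stopping rules: the 50% creatinine limb weakens in week two, and the individual triglyceride stop depends on an allocation the blinded investigator may not see

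*Combined protocol and SAP*

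**What the plan says.** **Creatinine.** Section 3.4.3.3 gives three limbs: above 120 µmol/L (stated to be 1.2 ULN), and two relative limbs, each introduced by "Or a change from baseline", of at least 30 µmol/L in 24 hours and at least 50% in one week. It cites KDIGO. Appendix 2 restates the relative limbs as a rise of at least 30 µmol/L "within 24h or Increase in serum creat to" 1.5 times baseline or more in 7 days. One subject meeting a limb is withdrawn; two in a cohort block escalation.

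**Baseline.** The stopping section does not define it. Section 9.3.4 does, under the qualifier "If not otherwise stated": "Baseline for safety parameters will be defined as the last available parameter value before and closest to the first dosing". For MAD creatinine that is D-1.

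**Schedule.** The Synopsis (Evaluation criteria, MAD) has "Laboratory evaluation: haematology, coagulation and biochemistry on D-1, D3, D6, D10 and D13 in the morning before dosing and D17 at discharge", plus follow-up. Under section 6.2, extra safety tests "may be added during the course of the study based on newly available data".

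**Triglycerides.** Section 3.4.3.2, added for the MAD part, stops an individual at 5.6 mmol/L or more only if he is receiving IFB-088, and stops the cohort when two subjects on IFB-088 reach that level. Appendix 2 gives the same threshold for one and two subjects with no allocation condition. Section 5.1 lets the investigator break the blind only in an emergency.

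**β2-microglobulin (B2M).** Section 3.4.3.3 uses the urinary B2M/creatinine ratio at twice normal; Appendix 2 gives B2M at 2 × ULN without the ratio.

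**The concern.** The kidney is the main non-clinical target organ. Section 1.3.2 records: "Preliminary toxicity studies pointed out renal findings after 10 or 14 days once a day administration". Those animals were dosed once daily at higher doses, and the timing reflects when they were examined. Even so, a rule that is strongest in the first week and weaker in the second is a poor match to 14 days of dosing. Because the same limbs feed the two-subject escalation rule, a rise that is missed in an individual is also not counted when the next dose is decided.

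The triglyceride rule raises a blinding problem. Following section 3.4.3.2 as written means someone must learn the subject's arm before deciding whether to stop him, and the decision then shows site staff what the arm is. Those staff are still attributing adverse events, which belong to the primary endpoint. The two texts also give opposite actions for a placebo subject at 5.6 mmol/L. Section 3.4.3.2 notes that some SAD subjects with raised triglycerides were on placebo.

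**Working it through.** **Schedule check.** The itemised MAD blood volumes in section 6.7.2 sum to the stated total: 18.7 + 10.2 + 96 + 32 + 10.2 + 10.2 + 24 + 10.2 + 10.2 + 96 + 56 + 16 + 10.2 + 10.2 = 410.1 mL. The items place on-treatment and discharge biochemistry on D3, D6, D10, D13 and D17 only.

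**Fixed baseline.** There is no Day 0, so these draws fall 3, 6, 10, 13 and 17 days after D-1. Only D3 and D6 lie within 7 days. Counting from D1 instead gives 2, 5, 9, 12 and 16 days, with the same result. Gaps between scheduled draws are 3, 3, 4, 3 and 4 days, so the 24-hour limb can work only on unscheduled repeats.

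**Rolling 7-day reading.** Assume a straight-line rise with R = D13 value / baseline, so the relative value on day t is f(t) = 1 + (R − 1)t/13. Take the largest ratio between two scheduled draws no more than 7 days apart, through D13. The >120 limb stays unmet for baselines up to 120/R.

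| R | D6 / D-1 (fixed) | Largest 7-day ratio (rolling) | >120 µmol/L unmet for baseline up to |
|---|---|---|---|
| 1.50 | 1.23 | 1.24 (D3 to D10) | 80 µmol/L |
| 1.65 | 1.30 | 1.30 (D3 to D10) | 72.7 µmol/L |
| 2.00 | 1.46 | 1.46 (D-1 to D6) | 60 µmol/L |
| 2.083 | 1.50 | 1.50 (D-1 to D6) | 57.6 µmol/L |

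Both readings first fire at R = 1 + 0.5 × 13/6 = 2.083. An exponential 1.5-fold rise by D13 also has a largest 7-day ratio of 1.24. The protocol's implied ULN is 120/1.2 = 100 µmol/L, so a baseline of 80 is well within normal.

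Example: 70 rising to 105 µmol/L by D13 (1.5-fold) meets no creatinine limb on either reading. A step is different. With 70 flat to D6 and 110 at D10 (110/70 = 1.57), the fixed reading misses it and the rolling reading catches it.

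**Effect of removing the 7-day limit.** Twice-daily dosing for 14 days is 28 doses. The D10 value reaches 1.5 when 1 + (R − 1) × 10/13 ≥ 1.5, that is R ≥ 1.65. A stop then spares 10 doses (D10 to D14) if acted on before the D10 dose, or 8 if acted on from D11. For R from 1.50 to under 1.65 the flag comes at D13 and spares 4 or 2 doses.

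**Triglycerides.** Section 5.4.1 gives blocks of 1:1, then 1 placebo to 5 active. One decision under section 3.4.3.2 therefore reveals 2 allocations if it concerns a first-block subject, all 6 of the second block if it concerns that block's placebo subject, and 1 if it concerns a second-block active subject.

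**The case against.** Several points on the other side have force.

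- *The D-1 baseline comes from a statistical default.* Section 9.3.4 concerns missing data and nothing links it to bedside withdrawal, while the rule itself cites KDIGO. That weakens the fixed reading but does not rescue the rule: the rolling reading is not stated either, and it misses the same straight-line rises.
- *Other protection continues.* The B2M/creatinine ratio and haematuria limbs, urea, eGFR, urinary protein and diuresis (section 1.3.2), the safety-signal clause in section 3.4.3 and investigator discretion (section 7.2) all remain, as does the 120 µmol/L limb at every draw. A reader might infer that renal monitoring lapses after D6; the documents do not support that.
- *The 24-hour limb.* Section 3.4.3.3 serves both parts and can act on repeat draws, so its lack of a scheduled MAD pair is not an error.
- *Rat exposure.* Table 6 reports for the 6 mg/kg/day group that "2 out of 10 males presented enlarged kidneys, with irregular colour and/or surface", with crystal nephropathy, at a day-90 male parent AUC of 23.6 ng/ml.h. Table 8 expects 25.57 and 42.62 in humans at 30 and 50 mg/day. A reader might infer that MAD doses reach a nephrotoxic exposure. Females in that group had a higher parent AUC (29.9) with no nephropathy listed, while metabolite AUC was 99.1 in males and 36.6 in females. Parent AUC does not track the lesion, so the comparison carries no weight here.
- *Appendix 2 is a summary.* It also drops qualifiers for vital signs, so section 3.4.3.2 may be meant to govern triglycerides. If so, the individual rule still needs allocation. The dose escalation committee may unblind for grade 3 findings, or for a treatment group with justification. However, the investigator is a member, and it is described as meeting before each subsequent dosing session, whereas this stop arises during dosing. Its charter, which might address this, is not available.

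**Conclusion.** The point stands in two parts. First, the relative creatinine limb reaches only D3 and D6 on the section 9.3.4 baseline. On either reading it misses straight-line rises from 1.50 to just under 2.08 times baseline by D13, provided baseline is low enough to keep the value at or below 120 µmol/L (80 or less for a 1.5-fold rise). This is a weaker numeric rule in week two. The result rests on an assumed smooth rise; the documents give no baseline creatinine values or time course, so its frequency cannot be estimated.

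Second, the individual triglyceride stop in section 3.4.3.2 depends on information the blinded investigator may obtain only in an emergency, and Appendix 2 disagrees with it. All SAD values were below 5.6 mmol/L, so it should rarely fire.

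The B2M difference might be read as a third conflict. It is probably summary shorthand: section 6.2 lists B2M only on urine, alongside urinary creatinine. It does not carry the finding.

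**What to change.** 1. **Creatinine (3.4.3.3, Appendix 2).** Apply at least 1.5 times the D-1 value at every on-study draw, with no 7-day limit. Keep the 24-hour limb, worded as a rise between any two draws within 24 hours, for unscheduled repeats. Cost: a few more stops for slow changes unrelated to drug, and a departure from the one-week limb that the protocol attributes to KDIGO.
2. **Triglycerides (3.4.3.2).** Stop any individual at 5.6 mmol/L or more regardless of arm, as Appendix 2 already reads. Have the existing unblinded pharmacist report only whether the criterion of two subjects on IFB-088 is met, and state that criterion in Appendix 2. Cost: an occasional placebo subject, one of two per cohort, is stopped and may need replacing. The cohort answer can also leak. With exactly two subjects at the limit, a yes implies both are on IFB-088 and a no implies at least one is on placebo.
3. **B2M (Appendix 2).** Write the urinary B2M/creatinine ratio, as a clerical alignment.

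This needs edits to three places and one instruction to the pharmacist, with no new scheduled draws, assays or staff.
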